6.5.2 Rescue Medications and Supportive Care

Participants should receive appropriate supportive care measures as deemed necessary by the treating investigator.

6.6 **Dose Modification**

6.6.1 Belzutifan Dosing Modifications

Guidelines for dose modification for belzutifan are listed in Table 3. Specific dose reduction levels are listed in Table 4.

The following should be considered in decisions regarding dose modifications:

- As a general approach, all AEs should be managed with supportive care at the earliest signs of toxicity considered related to belzutifan treatment. Should this be ineffective, dose reductions or interruptions should be considered to prevent worsening of toxicity.
- Dose reductions and/or interruptions, at any time while on study, should be implemented for unacceptable toxicity.
- Dose modifications or interruptions may also occur in the setting of lower grade toxicity than defined in Table 3, if the investigator feels it is in the interest of a participant's safety and will optimize drug tolerability.
- Interruption of belzutifan treatment for AEs may occur at any time per investigator discretion. An interruption of study treatment for >28 days will require Sponsor consultation.

The AE profile of belzutifan indicates that anemia and hypoxia have been associated with belzutifan treatment. Guidelines for the management of anemia and hypoxia are provided in Section 6.6.1.1 and Section 6.6.1.2, respectively. ECIs for belzutifan and guidelines for reporting these AEs as ECIs are provided in Section 8.4.7. Refer to the ECI Guidance (Appendix 8) for additional practice guidelines and management recommendations for AEs potentially related to belzutifan treatment.

Belzutifa	an-related Toxicity	Action			
Anemia	• Grade 4 anemia	 First episode: Hold belzutifan. Once toxicity has resolved to ≤Grade 2 or baseline, dose reduce belzutifan by one level. Second episode: Permanently discontinue belzutifan. 			
Neutropenia/Febrile neutropenia	 Grade 3 febrile neutropenia (ANC <1000/mm3 with a single temperature of >38.3 degrees C (101 degrees F) or a sustained temperature of >=38 degrees C (100.4 degrees F) for more than one hour,) or Grade 4 neutropenia for >5 days 	 First and second episodes: Hold belzutifan. Once toxicity has resolved to ≤Grade 2 or baseline, dose reduce belzutifan by one level. Third episode: Permanently discontinue belzutifan. 			
	• Grade 4 febrile neutropenia	• Permanently discontinue belzutifan.			
Thrombocytopenia	 Grade 3 thrombocytopenia with bleeding Grade 4 thrombocytopenia 	 First and second episodes: Hold belzutifan. Once toxicity has resolved to ≤Grade 2 or baseline, dose reduce belzutifan by one level. Third episode: Permanently discontinue belzutifan. First episode: Hold belzutifan. Once toxicity has resolved to ≤Grade 2 or baseline, dose reduce belzutifan by one level. Second episode: Permanently discontinue 			
Hypoxia Or Dyspnea	 Grade 3 dyspnea Grade 3 hypoxia (asymptomatic), belzutifan may be continued at the discretion of the investigator Grade 3 hypoxia (symptomatic) Grade 4 dyspnea 	 First and second episodes: Hold belzutifan. Once toxicity has resolved to ≤Grade 2 or baseline, dose reduce belzutifan by one level. Third episode: Permanently discontinue belzutifan. Permanently Discontinue belzutifan. 			
	Grade 4 hypoxia	- Termanentry Discontinue beizuttan.			
Gastrointestinal	• Grade 3 or 4 nausea, vomiting, or diarrhea if persistent for >48 hours despite optimal antiemetic or antidiarrheal therapy	 First and second episodes: Hold belzutifan. Once toxicity has resolved to ≤Grade 2 or baseline, dose reduce belzutifan by one level. Third episode: Permanently discontinue belzutifan. 			

Table 3	Dose Modification C	Juidelines for	Belzutifan-related	Toxicities
---------	---------------------	-----------------------	--------------------	------------

Belzutifan-related Toxicity		Action		
Hepatic	• Grade 3 increase in AST and/or ALT levels, if confirmed upon repeat testing within 48 hours	 First episode: Hold belzutifan. Once toxicity has resolved to ≤Grade 2 or baseline, dose reduce belzutifan by one level. Second episode: Permanently discontinue belzutifan. 		
	 Grade 4 increase in AST and/or ALT levels, if confirmed upon repeat testing within 48 hours, or Grade 3 or 4 increase in AST and/or ALT levels if accompanied by a Grade 2 increase in bilirubin level and an alkaline phosphatase level <2 × ULN 	• Permanently discontinue belzutifan.		
Cardiovascular, vascular, or thrombotic	• Grade 3 or 4 cardiovascular, vascular or thrombotic events	• Permanently discontinue belzutifan.		
Other Nonlaboratory Toxicities	• Any other nonlaboratory Grade 3 toxicity (excluding weight increased)	 First and second episodes: Hold belzutifan. Once toxicity has resolved to ≤Grade 2 or baseline, dose reduce belzutifan by one level. Third episode: Permanently discontinue belzutifan. 		
	• Any other nonlaboratory Grade 4 toxicity	• Permanently discontinue belzutifan.		
Other Laboratory Toxicities	• Grade 3 or 4 laboratory toxicity that does not resolve within 48 hours and is considered clinically significant by the investigator	• Permanently discontinue belzutifan.		
Abbreviations: ANC = abso = alanine aminotransfe Re-escalation to the next his resumed belzutifan at a	lute neutrophil count; $ULN = upper limitrase.gher dose level may be permitted after Spa given dose level for at least 28 days and$	t of normal; AST = aspartate aminotransferase; ALT ponsor Consultation for a participant that has l original toxicity has not reappeared.		

Re-escalation of belzutifan will not be permitted for events of Grade 3 symptomatic hypoxia.

If action is "dose reduce by one dose level" and participant is already at dose level -2 when a toxicity occurred, belzutifan should be permanently discontinued.

Dose Level	Dose
Starting Dose	120 mg QD
-1	80 mg QD
-2	40 mg QD

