7 DISCONTINUATION OF STUDY INTERVENTION AND PARTICIPANT WITHDRAWAL

7.1 Discontinuation of Study Intervention

Discontinuation of study intervention does not represent withdrawal from the study.

As certain data on clinical events beyond study intervention discontinuation may be important to the study, they must be collected through the participant's last scheduled followup, even if the participant has discontinued study intervention. Therefore, all participants who discontinue study intervention prior to completion of the protocol-specified treatment period will still continue to participate in the study as specified in Section 1.3 and Section 8.11.3.

Participants may discontinue study intervention at any time for any reason or be discontinued from the study intervention at the discretion of the investigator should any untoward effect occur. In addition, a participant may be discontinued from study intervention by the investigator or the Sponsor if study intervention is inappropriate, the study plan is violated, or for administrative and/or other safety reasons. Specific details regarding procedures to be performed at study intervention discontinuation are provided in Section 8.1.9 and Section 8.11.3.

A participant must be discontinued from study intervention, but continue to be monitored in the study for any of the following reasons:

- The participant or participant's legally acceptable representative requests to discontinue study intervention.
- Radiographic disease progression outlined in Section 8.2.1 (exception if the Sponsor approves treatment continuation following BICR-verified disease progression per RECIST [Section 4.1]).
- Any progression or recurrence of any malignancy, or any occurrence of another malignancy that requires treatment.
- Unacceptable AEs or toxicities (Section 6.6).
- The participant interrupts study intervention administration for >28 consecutive days without Sponsor consultation.
- The participant has a medical condition or personal circumstance which, in the opinion of the investigator and/or Sponsor, placed the participant at unnecessary risk from continued administration of study intervention.
- The participant has a confirmed positive serum or highly sensitive urine pregnancy test.
- Sponsor discontinuation of study.

As described in Section 4.1, treatment may continue beyond BICR-verified disease progression, but requires Sponsor consultation and approval. If approved by the Sponsor,

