8.4.7 Events of Clinical Interest

Selected nonserious and SAEs are also known as ECIs and must be reported to the Sponsor. ECIs that are not SAEs should be collected through 30 days following cessation of study intervention and must be reported by the investigator. ECIs that are SAEs should be collected through 90 following cessation of study intervention and must be reported by the investigator.

Events of clinical interest for this study include:

- a. An overdose of Sponsor's product, as defined in Section 8.5.
- b. Potential DILI events defined as an elevated AST or ALT laboratory value that is greater than or equal to 3X the upper limit of normal and an elevated total bilirubin laboratory value that is greater than or equal to 2X the upper limit of normal and, at the same time, an alkaline phosphatase laboratory value that is less than 2X the upper limit of normal, as determined by way of protocol-specified laboratory testing or unscheduled laboratory testing.*

*Note: These criteria are based upon available regulatory guidance documents. The purpose of the criteria is to specify a threshold of abnormal hepatic tests that may require an additional evaluation for an underlying etiology. The study site guidance for assessment and follow-up of these criteria can be found in the Investigator Study File Binder (or equivalent).

- c. Any ≥Grade 3 anemia
- d. Any ≥Grade 3 hypoxia
- e. Any ≥Grade 3 AE deemed related to belzutifan by the investigator, including laboratory abnormalities

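### Table 3's combined liver-injury stop is automatic with Grade 2 bilirubin but, read literally, only conditional with Grade 3 or 4 bilirubin

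*Protocol*

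**What the plan says.** Protocol Section 6.6.1, Table 3, deals with liver enzymes in two Hepatic entries.

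- The first is "Grade 3 increase in AST and/or ALT levels, if confirmed upon repeat testing within 48 hours". A first episode means holding belzutifan and, once recovered to Grade 2 or below or to baseline, restarting one dose level lower. A second episode is a permanent stop. Bilirubin is not mentioned.
- The second is a permanent stop with two triggers: confirmed Grade 4 AST/ALT, or "Grade 3 or 4 increase in AST and/or ALT levels if accompanied by a Grade 2 increase in bilirubin level" with ALP below 2 × ULN.

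Further down, the Other Laboratory Toxicities row requires a permanent stop for "Grade 3 or 4 laboratory toxicity that does not resolve within 48 hours and is considered clinically significant by the investigator".

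Two notes to the table also matter. Where the action is a one-level reduction and the "participant is already at dose level -2 when a toxicity occurred, belzutifan should be permanently discontinued". Re-escalation may be allowed after at least 28 days at a dose, with Sponsor consultation, and the only event excluded is the one in "Re-escalation of belzutifan will not be permitted for events of Grade 3 symptomatic hypoxia".

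Section 8.4.7(b) defines potential drug-induced liver injury with an open-ended bilirubin limit: "elevated total bilirubin laboratory value that is greater than or equal to 2X the upper limit of normal". That is a reporting rule with no dosing action. Its note adds: "The study site guidance for assessment and follow-up of these criteria can be found in the Investigator Study File Binder".

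**The concern.** The combined trigger names one bilirubin grade. A rule for combined liver injury should become stricter, or at least no looser, as bilirubin rises. Read literally, this one does the reverse in one corner: the milder bilirubin rise closes off belzutifan for good, and the worse one leaves that decision to other rows and to judgement.

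What is at stake is participant safety in the belzutifan arm, specifically whether a restart stays open. From 120 mg the restart would be at 80 mg, and from 80 mg at 40 mg. Later re-escalation is not ruled out for liver events. Sites should not have to correct the wording of a stopping rule in order to apply it safely.

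**Working it through.** No figure in the plan bears on this, so the check is to apply Table 3 as a set of rules.

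**Are the grades in this row exact or minimum values?** The bullet itself writes Grade 3 or 4 for AST/ALT, where both are meant, and then a single grade for bilirubin. Grade 3 and Grade 4 AST/ALT alone have separate entries with different actions. Where the protocol means a minimum elsewhere it uses the ≥ sign, as for anemia and hypoxia in Section 8.4.7. The literal reading is therefore an exact grade.

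**Outcome for a first confirmed Grade 3 AST/ALT rise, ALP below 2 × ULN, at 120 mg or 80 mg:**

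| Bilirubin | Hepatic row | Whole of Table 3 |
|---|---|---|
| Grade 0–1 | Hold, restart one level lower | Same |
| Grade 2 | Permanent stop | Permanent stop, no further condition |
| Grade 3–4 | Hold, restart one level lower | Permanent stop if unresolved at 48 hours and judged clinically significant; otherwise as in the Hepatic row |

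**How wide is the gap?** Enumerate AST/ALT grade (3, 4) × bilirubin grade (2, 3, 4) × episode (first, second) × dose (120, 80, 40 mg), with AST/ALT confirmed and ALP below 2 × ULN throughout: 2 × 3 × 2 × 3 = 36 combinations.

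- Grade 4 AST/ALT: 3 × 2 × 3 = 18, all permanent stops.
- Grade 3 AST/ALT with Grade 2 bilirubin: 2 × 3 = 6, all permanent stops.
- Grade 3 AST/ALT with Grade 3 or 4 bilirubin, second episode: 2 × 3 = 6, all permanent stops.
- The same, first episode, already at 40 mg: 2, both permanent stops under the dose level -2 note.
- The same, first episode, at 120 or 80 mg: 2 × 2 = 4, where the stop is conditional.

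Unconditional stops: 18 + 6 + 6 + 2 = 32. Conditional: 36 − 32 = 4. With ≥Grade 2 in the bilirubin condition, all 36 become unconditional stops.

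These are outcomes of the rules. The combinations are not equally likely, and the documents give nothing from which to derive how often the four would occur.

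**Does another provision close the four?**

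- Section 7.1 requires discontinuation for unacceptable toxicity but refers back to Section 6.6, so it adds no separate threshold.
- Appendix 8 gives management steps for anemia and hypoxia only.
- The rechallenge note in Appendix 3 (Section 10.3.5) requires advance Sponsor approval for some rechallenges. It does not prohibit them.
- Section 8.4.7(b) governs reporting. Its open-ended limit suggests that a minimum was intended in Table 3 too, but it sets no dosing action.

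**The case against.** A reader might infer that Table 3 simply allows restart after the worse bilirubin rise. The documents do not support that. Bilirubin has no trigger of its own in the Hepatic row, so a Grade 3 or 4 rise can fall under Other Laboratory Toxicities. Restart then remains open only if the rise resolves within 48 hours, if the investigator judges it not clinically significant, or if a site takes that row to exclude liver tests. This narrows the point to automatic against conditional. It does not remove it.

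Four further arguments deserve weight.

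- **Grades as minimum values.** Section 6.6.1 says modifications may also be made at grades lower than Table 3 defines, which gives some support to reading the listed grades as minimum triggers. Many physicians would read Grade 2 bilirubin that way. The sentence grants discretion, however, and the table states no minimum here.
- **Sponsor oversight.** Potential drug-induced liver injury is reported within 24 hours, interruptions beyond 28 days need Sponsor consultation, and rechallenge needs advance approval where the event was serious and possibly drug-caused or where re-exposure poses added significant risk. An unapproved restart is therefore less likely, but these are case-by-case judgements, whereas Grade 2 bilirubin triggers a fixed rule.
- **A lost symbol.** A ≥ sign is visibly garbled in one bullet of Section 10.8.2, and other words in Table 3 are damaged. Against that, ≤Grade 2 and <2 × ULN survive in the same table. A lost sign can be neither shown nor excluded from this text.
- **Unseen guidance.** The site guidance cited in the note to Section 8.4.7(b) is not among these documents and may already cover the case.

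**Conclusion.** The point holds in a limited form. On the text available, the permanent stop is automatic for Grade 2 bilirubin and conditional for Grade 3 or 4 bilirubin. This applies to a first confirmed Grade 3 AST/ALT rise with ALP below 2 × ULN at two of the three dose levels (120 and 80 mg). Nothing in the documents gives a reason for treating the higher grade less strictly, and ≥Grade 2 is probably what was meant.

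A reader might also infer that dosing continues through such an event, or that trial results are affected. Neither follows: belzutifan is held in every case, and no endpoint, sample size or analysis is touched. The frequency is probably low. The conclusion assumes that the bare Grade 2 is what the source document prints and that the site guidance does not override it. Confidence is medium for those two reasons. The change is still worth making because this is a working stopping rule for liver injury.

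**What to change.** First check the source document for a ≥ sign at this spot, and check the site guidance cited in the note to Section 8.4.7(b). If the sign is absent, amend the bilirubin condition in Table 3 (Hepatic) to ≥Grade 2 at the next amendment and send sites a short clarifying memo now. If the site guidance already sets that minimum, align the table with it. The cost is one symbol in one table row plus the memo, with no added procedures and no change to any analysis.

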6.6.1.1 Management of Anemia

Participants enrolled in the study will have a baseline hemoglobin level of ≥ 10 g/dL (no transfusion or growth factor support within 4 weeks of the hematology screening assessment). During the study, participants should undergo hematology assessments at each clinic visit (Appendix 2) to monitor their hemoglobin and hematocrit to detect onset or worsening of anemia. If clinically indicated, anemia will be appropriately managed by the investigator. Given that decreased EPO is the etiology of potential anemia with belzutifan treatment, EPO replacement is an effective management strategy for participants who may develop and subsequently require intervention for belzutifan-induced anemia. Transfusion can also be used to manage anemia in patients receiving belzutifan.

6.6.1.2 Management of Hypoxia

Participants enrolled in the study will have a baseline pulse oximetry of at least 92% at rest, nor require intermittent or chronic supplemental oxygen. During the study, participants undergo pulse oximetry monitoring at each clinic visit (Section 1.3). If clinically indicated, management of hypoxia should include treating any underlying acute medical conditions and providing supplemental oxygen therapy as necessary. Diagnosis of hypoxia is to follow CTCAE v5 and management to follow the dose modification Table 3 and ECI guidance in Appendix 8.

6.6.2 Everolimus Dosing Modifications

For participants on the everolimus arm, dose adjustments and the management of AEs should be made as described in the everolimus package insert.

6.7 Intervention After the End of the Study

There is no study-specified intervention after the end of the study.

6.8 Clinical Supplies Disclosure

This study is open-label; therefore, the participant, the study-site personnel, the Sponsor, and/or designee are not blinded. Study intervention (belzutifan and everolimus) is included in the label text; random code/disclosure envelopes or lists are not provided.

6.9 Standard Policies

For studies using controlled substances, all Federal, State, Province, Country, etc, regulations must be adhered to in regard to their shipping, storage, handling, and dispensing of controlled substances. Additionally, the investigator should have the appropriate controlled drug license(s) as mandated by Federal, State, Province, Country, etc, laws in which the study is being conducted.

6.9.1 Study Site Retention Samples

Not applicable

MK-6482-005-09 FINAL PROTOCOL

7 DISCONTINUATION OF STUDY INTERVENTION AND PARTICIPANT WITHDRAWAL

7.1 Discontinuation of Study Intervention

Discontinuation of study intervention does not represent withdrawal from the study.

As certain data on clinical events beyond study intervention discontinuation may be important to the study, they must be collected through the participant's last scheduled followup, even if the participant has discontinued study intervention. Therefore, all participants who discontinue study intervention prior to completion of the protocol-specified treatment period will still continue to participate in the study as specified in Section 1.3 and Section 8.11.3.

Participants may discontinue study intervention at any time for any reason or be discontinued from the study intervention at the discretion of the investigator should any untoward effect occur. In addition, a participant may be discontinued from study intervention by the investigator or the Sponsor if study intervention is inappropriate, the study plan is violated, or for administrative and/or other safety reasons. Specific details regarding procedures to be performed at study intervention discontinuation are provided in Section 8.1.9 and Section 8.11.3.

A participant must be discontinued from study intervention, but continue to be monitored in the study for any of the following reasons:

- The participant or participant's legally acceptable representative requests to discontinue study intervention.
- Radiographic disease progression outlined in Section 8.2.1 (exception if the Sponsor approves treatment continuation following BICR-verified disease progression per RECIST [Section 4.1]).
- Any progression or recurrence of any malignancy, or any occurrence of another malignancy that requires treatment.
- Unacceptable AEs or toxicities (Section 6.6).
- The participant interrupts study intervention administration for >28 consecutive days without Sponsor consultation.
- The participant has a medical condition or personal circumstance which, in the opinion of the investigator and/or Sponsor, placed the participant at unnecessary risk from continued administration of study intervention.
- The participant has a confirmed positive serum or highly sensitive urine pregnancy test.
- Sponsor discontinuation of study.

As described in Section 4.1, treatment may continue beyond BICR-verified disease progression, but requires Sponsor consultation and approval. If approved by the Sponsor,

continued participation requires additional consent (Section 8.1.1). Participants who continue treatment beyond confirmed disease progression will continue with all protocol-specified assessments and procedures.

7.2 Participant Withdrawal From the Study

A participant must be withdrawn from the study if the participant or participant's legally acceptable representative withdraws consent from the study.

If a participant withdraws from the study, they will no longer receive study intervention or be followed at scheduled protocol visits.

Specific details regarding procedures to be performed at the time of withdrawal from the study, as well as specific details regarding withdrawal from FBR, are outlined in Section 8.1.9. The procedures to be performed should a participant repeatedly fail to return for scheduled visits and/or if the study site is unable to contact the participant are outlined in Section 7.3.

7.3 Lost to Follow-up

If a participant fails to return to the clinic for a required study visit and/or if the site is unable to contact the participant, the following procedures are to be performed:

The site must attempt to contact the participant and reschedule the missed visit. If the participant is contacted, the participant should be counseled on the importance of maintaining the protocol-specified visit schedule.

The investigator or designee must make every effort to regain contact with the participant at each missed visit (eg, telephone calls and/or a certified letter to the participant's last known mailing address or locally equivalent methods). These contact attempts should be documented in the participant's medical record.

Note: A participant is not considered lost to follow-up until the last scheduled visit for the individual participant. The missing data for the participant will be managed via the prespecified statistical data handling and analysis guidelines.

